#### Cycle 1 (28-day cycle)

- Daratumumab 1800 mg SC on days 1, 8, 15, and 22
- Clarithromycin 500 mg PO bid continuous 1-28 days until VGPR achieved
- Pomalidomide 4 mg PO on days 1-21 of 28-day cycle
- Dexamethasone 20 mg IV will be administered as a premedication prior to daratumumab injection on days 1 and 8, 20 mg PO will be administered the day after daratumumab dosing on days 2 and 9 (total of 40 mg/week)\*\*, 40 mg PO will be administered as a premedication prior to daratumumab injection on days 15 and 22

#### Cycles 2-6 (28-day cycle)

- Daratumumab 1800 mg SC on days 1, 8, 15, and 22 for Cycle 2 and Daratumumab 1800 mg SC q2wk days 1 & 15 Cycles 3-6
- Clarithromycin 500 mg PO bid continuous days 1-28 (if <VGPR and discontinued if VGPR achieved)
- Pomalidomide 4 mg PO on days 1-21 of 28-day cycle

- Dexamethasone 40 mg PO will be administered as a premedication prior to daratumumab injection weekly for Cycle 2 and biweekly for Cycles 3-6
- Dexamethasone 40 mg PO weekly on non-daratumumab treatment days (Cycles 3-6)

#### Cycles 7-8 (28-day cycle)

- Daratumumab 1800 mg SC q4wks on Day 1
- Clarithromycin 500 mg PO bid days continuous 1-28 (if <VGPR and discontinued if VGPR achieved)
- Pomalidomide 4 mg PO on Days 1-21 of 28-day cycle
- Dexamethasone 20 mg PO will be administered as a premedication prior to daratumumab injection on day 1 of daratumumab (Cycles 7-8)
- Dexamethasone 20 mg PO weekly on non-daratumumab treatment days

#### Cycles 9-30 Maintenance (28-day cycle)

- Daratumumab 1800 mg SC q4wks on Day 1
- Pomalidomide 4 mg PO on Days 1-21 of 28-day cycle
- Dexamethasone 20 mg PO will be administered as a premedication prior to daratumumab injection on day 1 of daratumumab.
- Dexamethasone 20 mg PO weekly on non-daratumumab treatment days

During the study, assessments will be performed as shown in the Study Calendar and as clinically indicated.

**\*\*Dexamethasone dosing if  $\geq 70$  year old- decrease dex dose by 50% in induction:**  
 10 mg IV as premed on days 1 and 8 and 20mg PO on days 15 and 22 (Cycle 1) 10 mg PO the day after daratumumab on day 2 and 9 for Cycle 1 (total 20 mg/week)  
 20 mg PO as premedication weekly for cycle 2  
 20 mg PO weekly (cycles 3-6); 10 mg PO weekly (cycles 7+)

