## Protocol Summary

Full Title:	A PHASE II STUDY OF DARATUMUMAB, CLARITHROMYCIN, POMALIDOMIDE AND DEXAMETHASONE (D-ClaPd) IN MULTIPLE MYELOMA PATIENTS PREVIOUSLY EXPOSED TO DARATUMUMAB
Short Title:	D-ClaPd IN REL/REF MULTIPLE MYELOMA
Clinical Phase:	2
Principal Investigator:	[name] [name]
Study Description:	This single-arm phase 2 study will test the hypothesis that in patients with previous daratumumab exposure, daratumumab in combination with ClaPd will yield higher $\geq$ VGPR rates in historical pomalidomide/dexamethasone.
Sample Size:	N= 40
Enrollment:	This study will enroll 40 subjects and screen up to 44 subjects.
Study Population:	Patients will be over 18 years of age with relapsed/refractory multiple myeloma. Patients who have received 1 or more prior lines of therapy which must include daratumumab and may include ASCT are eligible. The patient must have received both an IMiD and PI in prior lines. Prior pomalidomide exposure in 1 or more previous lines of therapy allowed if PR or better achieved. No disease progression may have occurred within 60 days of receiving pomalidomide. Patient may be daratumumab refractory (i.e less than a PR) achieved on prior daratumumab-based therapy or have exhibited progression within 60 days of receiving daratumumab.
Study Design:	This is a single-center single-arm phase 2 study in which 40 patients will receive daratumumab in combination with clarithromycin/pomalidomide/dexamethasone until PD or unacceptable toxicity, whichever comes first. Patients will be treated for 8 cycles of therapy with continuation of maintenance daratumumab/pomalidomide if evidence of PR or better.

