## Facilities Enrolling

**Participants:**

Weill Cornell Medical College-NewYork Presbyterian Hospital (WCMC/NYPH), Brooklyn Methodist Hospital (BMH), and NewYork-Presbyterian Queens (NYPQ)

Participant Duration:	Time it will take for each individual participant to complete all participant visits in the induction phase is 8 months. Patients who complete all 32 cycles of treatment for the entire study, if have not progressed or started new treatment, will be followed with disease evaluations every 90 days (+/- 30 days) until confirmed disease progression or for total duration of 24 months from last EOT visit, whichever comes first, and for survival for up to 10 years from date of enrollment or until death.
Study Agent/Device Name	
Intervention Description:	
Induction Phase (Cycles 1-8, q28 day cycles):
 
 
• Daratumumab 1800 mg SC weekly x 8 wks, 1800 mg SC q2wk days 1 and 15 (cycles 3-6) 1800 mg SC q4wk day 1 (cycles 7-8)
 
• Clarithromycin 500mg PO bid continuous until VGPR or 8 cycles, whichever occurs first
 
• Pomalidomide 4 mg PO days 1-21
 
• Dexamethasone 20 mg IV as premed days 1 and 8 (cycle 1); 20 mg PO days 2 and 9 (cycle 1); 40 mg PO as premed days 15 and 22 (cycle 1); 40 mg PO qwk (cycles 2-6); 20 mg PO qwk (cycles 7-8)
 
 
Maintenance Phase (Cycle 9+): up to 24 months q28 day cycles
 
 
• Daratumumab 1800 mg SC day 1
 
• Pomalidomide 4 mg PO days 1-21
 
• Dexamethasone 20 mg PO qwk
 

Primary Objective:	PRIMARY: To determine best response rate within 8 cycles of induction therapy.
Secondary Objectives:	SECONDARY: To determine median PFS and OS, time to response (TTR), time to progression (TTP), response duration, time to next therapy (TTNT), time to $\geq$ VGPR, ORR, CR or better rate, MRD negativity rate after 8 and 32 months, AEs in induction and maintenance phases, clinical response in high-risk groups.
Exploratory Objectives:	Assessment of MRD by multiparameter flow cytometry (MFC), FISH, NGS, PET/MRI imaging studies at best response. MFC-based tests of BM aspirates of both CD138-isolated clonal plasma cells and immune cells from marrow and tissue will be studied for various immune-based and daratumumab-based markers; dose-intensity analyses (mean relative dose intensity of dexamethasone); QoL assessments.
Endpoints:	Primary Endpoint:

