### SCHEDULE OF STUDY PROCEDURES

Screening Phase  Day-28 to 0		Treatment	End of Treatm	Post-Treatment Observation Phase
		(Cycle is 28 days) +/- 3 days for Cycle 1 and 2, +/- 7 days for Cycles 3-30	At 1 year (+/- 7 days) & 90 days after last dose of study drug (+/-7 days)	Each cycle is 90 days, +/- 30 days for 24 months or until progression
Informed consent a	X			
Inclusion/exclusion criteria review	X			
Demography/Medical history	X			
Physical Exam	X	X b (every cycle)	X	
Vital signs c	X	X d (every cycle)	X	
Weight	X	X (every cycle)	X	
ECOG status	X	X (every cycle)	X	
ECG	X			
Echocardiogram	X		X	
Pulmonary function testing e	X e		X e	
Chest x-ray f				
NYHA classification	X	X (cycle 1 only)	X	
Patient Diary g	X	X (every cycle)	X	
Concomitant medications	Continuous from time of ICF until 30 days of last treatment			
Adverse events	Continuous from time of ICF until 30 days of last treatment			
Study Drug Administration				
Daratumumab 1800 mg SC dosing h		Daratumumab 1800 mg SC on Days 1, 8, 15, and 22 of Cycles 1 and 2 (weekly dosing), on Days 1 and 15 of Cycles 3 to 6 (every 2 weeks dosing), and on Day 1 of Cycle 7 and subsequent cycles (every 4 weeks dosing)		

Clarithromycin		500 mg PO bid continuous days 1-28 of cycles 1-8 only		
Pomalidomide		Pomalidomide 4 mg PO days 1-21		

Dexamethasone		Dexamethasone (Cycle 1 D1 & 8): 20 mg IV Cycle 1 D2 & D9: 20mg PO Cycle 1 D15 & D22: 40mg PO Cycles 2- 6: 40 mg PO qwk Cycles 7- 8: 20mg PO qwk Cycle 9+: 20mg PO qwk		
Prophylactic Medications				
Varicella Zoster Prophylaxis		Valacyclovir 500mg PO qd (or equivalent, renally dosed-adjusted)		
Gastrointestinal Prophylaxis		Pantoprazole 40 mg PO daily, or other		
Laboratory Assessments				
Pregnancy test i	X	X	X	
Blood typing/indirect antiglobulin test	X			
Hematology (CBC) with differential	X	On Days 1, 8, 15, and 22 for Cycles 1 and 2; On Days 1 and 15 for Cycles 3 through 6; D1 from Cycle 7 onward and as clinically indicated	X	
Serum chemistry j	X	On Days 1, 8, 15, and 22 for Cycle 1-2, Day 1, 15 for cycles 3-6 and day 1 of each subsequent cycle	X	
Hepatitis B and C screening k	X	HBV DNA monitoring q12weeks	X	X i
Disease Assessments				
Serum $\beta$ 2-microglobulin	X			
Serum free light chains	X	X (every cycle)	X	X (every cycle)

SPEP and IFE	X	X (every cycle)	X	X (every cycle)

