3.3.4 Imaging (PET/MRI) at diagnosis and at best response/MRD

3.3.5 Dose intensity analysis (mean relative dose intensity of dexamethasone)

## 4. STUDY DESIGN

### 4.1 Overview of Study Design

This is a single center, single-arm phase 2 study that will be conducted at Weill Cornell Medical College to evaluate the best response within 8 cycles of induction in relapsed/refractory multiple myeloma compared to historical pomalidomide/dexamethasone. Patients will receive daratumumab/clarithromycin/ pomalidomide/dexamethasone (D-ClaPd) for 8 cycles of induction followed by daratumumab/pomalidomide/dexamethasone for maintenance until PD or unacceptable toxicity, whichever comes first. Patients will be treated for up to 24 months of maintenance if evidence of PR or better after induction.

D-ClaPd has potential for synergistic activity with good tolerability/safety in relapsed/refractory myeloma.

In patients with previous daratumumab exposure, the following hypotheses will be tested:

- D-ClaPd will yield higher  $\geq$ VGPR rates in relapsed/refractory myeloma than historical pomalidomide/dexamethasone ( $\geq$ VGPR 9%) in this setting.
- Daratumumab retreatment in combination with ClaPd in early relapse will have higher ORR than ClaPd (ORR 60%).

Patient participation will include a screening phase and a treatment phase. The screening phase will be up to 28 days prior to first dose of study drug. The Treatment Phase begins on the date of the first study treatment and ends on the date the patient and the investigator agree that the patient will no longer continue study treatment.

During the treatment phase, daratumumab, clarithromycin, pomalidomide, and dexamethasone will be administered as per the following schedule.

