#### 6.2.4 Dexamethasone Administration

For Cycle 1, 20mg IV dexamethasone will be administered as a premedication on days 1 and 8 and 20 mg PO will be administered on days 2 and 9 (40mg weekly)\*\*; 40mg PO will be administered as premedication on days 15 and 22.

For Cycles 2-6, 40 mg PO dexamethasone will be administered weekly.

For Cycles 7-8, 20mg PO dexamethasone will be administered weekly.

For Cycle 9+, 20mg PO dexamethasone will be administered weekly.

When dexamethasone is administered on daratumumab treatment days, dexamethasone should be administered as a premedication prior to daratumumab injection.

\*\*Dexamethasone dosing if  $\geq 70$  years old- decrease dex dose by 50% in induction:

10 mg IV as premed on days 1 and 8 and 20mg PO on days 15 and 22 (Cycle 1)

10 mg PO the day after daratumumab on days 2 and 9 for Cycle 1 (total 20 mg/week)

20 mg PO as premedication weekly for cycle 2

20 mg PO weekly (cycles 3-6); 10 mg PO weekly (cycles 7+)

When taken orally, dexamethasone should be taken with food or milk to avoid gastrointestinal side effects. Missed doses can be taken as soon as the patient remembers if the next scheduled dose is 72 hours or more away. A double dose should not be taken to make up for a missed dose. If the patient vomits after taking a dose, the patient should not repeat the dose but should resume dosing at the time of the next scheduled dose.

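### For patients aged 70 or over, the dexamethasone reduction is confined to induction by its heading but runs into maintenance by its cycle range, so two written maintenance doses differ 1.6- to 2.0-fold

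*Combined protocol and SAP*

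**What the plan says.** - **Age rule.** Section 4.1, after the Cycles 9-30 block, and again Section 6.2.4: for patients aged 70 or over, "decrease dex dose by 50% in induction". The closing dose line under that heading reads "20 mg PO weekly (cycles 3-6); 10 mg PO weekly (cycles 7", with a plus sign after the 7, so the range has no upper end. The rule also sets a 10 mg IV premedication on days 1 and 8 of cycle 1.
- **Induction.** The Protocol Summary (Intervention Description) defines it as cycles 1-8.
- **Maintenance dose.** The Protocol Summary lists "Dexamethasone 20 mg PO qwk"; the Schedule of Study Procedures has "Cycle 9+: 20mg PO qwk"; the Cycles 9-30 block of Section 4.1 has 20 mg as premedication on day 1 and "Dexamethasone 20 mg PO weekly on non-daratumumab treatment days"; Section 6.2.4 has "For Cycle 9+, 20mg PO dexamethasone will be administered weekly". None has an age exception.
- **Maintenance regimen.** The overview in Section 4.1 describes "daratumumab/pomalidomide/dexamethasone for maintenance until PD or unacceptable toxicity". The Study Design entry of the Protocol Summary instead speaks of "continuation of maintenance daratumumab/pomalidomide if evidence of PR or better", without naming dexamethasone.
- **Premedication.** Section 6.2.1.2 lists dexamethasone 20 mg before every daratumumab injection for all patients. The note to Table 6-4 keeps that 20 mg whatever dexamethasone reductions have been made.

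**The concern.** The heading of the age rule and the last line beneath it cannot both hold. Going by the heading, the reduction ends with cycle 8 and the general 20 mg weekly applies from cycle 9. Going by the cycle range, 10 mg weekly continues through maintenance. Section 6.2.4 contains both instructions within one section.

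The consequences for the analysis fall on the maintenance phase. Improvement in response during maintenance is a secondary endpoint (Section 3.2), and adverse events in maintenance are a secondary objective in the Protocol Summary. Both could pool patients of the same age on different steroid schedules, depending on which line the prescriber followed. Section 3.3.5 plans a mean relative dose intensity for dexamethasone, which needs one planned dose per patient and cycle. With three facilities listed as enrolling, different readings are plausible, and there is no single standard for judging adherence.

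**Working it through.** **1. Does the stated 50% reproduce within induction?** Milligrams per 28-day cycle, from Sections 4.1 and 6.2.4:

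| Cycle | Under 70 | 70 or over | Ratio |
|---|---|---|---|
| 1 | (20 + 20) × 2 + 40 × 2 = 160 | (10 + 10) × 2 + 20 × 2 = 80 | 0.50 |
| 2-6, each | 40 × 4 = 160 | 20 × 4 = 80 | 0.50 |
| 7-8, each | 20 × 4 = 80 | 10 × 4 = 40 | 0.50 |
| Total, cycles 1-8 | 160 + 5 × 160 + 2 × 80 = 1,120 | 80 + 5 × 80 + 2 × 40 = 560 | 0.50 |

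The 50% reproduces in every cycle. On the weekly doses, heading and dose lines agree up to cycle 8 and part at cycle 9.

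**2. Maintenance dose per cycle, age 70 or over.** Four weekly doses, with daratumumab on day 1 only.

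- Reading A (heading governs): 4 × 20 = 80 mg.
- Reading B (cycle range governs): 4 × 10 = 40 mg. A/B = 80/40 = 2.0.
- Reading C (cycle range governs, with the 20 mg premedication kept on day 1): 20 + 3 × 10 = 50 mg. A/C = 80/50 = 1.6.

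**3. Planned totals if every maintenance cycle is completed.**

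| | A | B | C |
|---|---|---|---|
| Cycles 9-30 (22 cycles) | 1,760 mg | 880 mg | 1,100 mg |
| Cycles 9-32 (24 cycles) | 1,920 mg | 960 mg | 1,200 mg |

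The second row is shown because the Protocol Summary and Section 7.4 refer to 32 cycles.

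**4. Relative dose intensity = dose given / dose planned, per cycle.**

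| Given | Planned A (80) | Planned B (40) | Planned C (50) |
|---|---|---|---|
| 10 mg weekly (40 mg) | 50% | 100% | 80% |
| 20 mg weekly (80 mg) | 100% | 200% | 160% |

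The same record scores 50% or 100%, or 100% or 200%, according to the line chosen as the plan.

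**5. Premedication.** The age rule's 10 mg premedication on days 1 and 8 of cycle 1 also disagrees with the 20 mg in Section 6.2.1.2 and the Table 6-4 note. The documents do not say whether that note covers the age-based reduction as well as reductions for adverse events. Readings B and C are therefore both shown.

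**The case against.** The best reply is that a specific rule overrides a general one. The protocol gives general doses and then one age footnote, and the footnote's 10 mg line appears identically in two sections. It is also fair that the missing age exception in the maintenance blocks proves little: the blocks for cycles 2-6 and 7-8 have none either, although the age rule plainly applies there. That part stands, and it narrows the conflict to heading against cycle range. It does not resolve it, because the limit to induction belongs to the specific rule itself.

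Second, maintenance doses will vary anyway, since Tables 6-4 and 6-5 allow reductions and Section 6.3 calls its provisions guidelines. True, but variation in the dose given does not supply the planned dose against which intensity is measured.

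A reader might draw three stronger conclusions that the documents do not support:

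- *That zero dexamethasone is a third written maintenance dose.* The Study Design sentence only leaves the drug out and does not tell anyone to stop it. The same Protocol Summary, the Schedule, and Sections 4.1 and 6.2.4 all include it. It is an incomplete label that should be aligned.
- *That the gap is always exactly twofold.* That ignores the premedication provisions, under which it may be 1.6-fold.
- *That about half the patients are affected.* The median age of 69 in Section 1.1 describes myeloma generally. The documents give neither this trial's age mix nor the number expected to reach maintenance, which requires a partial response or better.

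**Conclusion.** The contradiction is real, confined to patients aged 70 or over, and starts at cycle 9. The size is 80 against 40 mg per cycle, or 80 against 50 mg if the 20 mg premedication applies to this age group. The totals in the working are ceilings, since they assume completion of every maintenance cycle. The number of patients affected cannot be derived from the documents.

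The primary endpoint is best response within 8 cycles, so neither its definition nor the 8-of-40 decision rule changes. What is affected is maintenance exposure and safety, improvement in response during maintenance, and the exploratory dose-intensity analysis. The separate mismatch over 10 mg or 20 mg premedication in this age group needs settling at the same time. No view is taken on which dose is right.

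**What to change.** Issue a clarifying amendment that reconciles the following into one statement of maintenance dexamethasone by age group: the Protocol Summary (Study Design and Intervention Description), the Schedule of Study Procedures, the Cycles 9-30 block and age rule in Section 4.1, Section 6.2.1.2, Section 6.2.4, and the note to Table 6-4. Within the age rule, make the heading and the cycle range agree, and say whether the 20 mg premedication applies to patients aged 70 or over. Name dexamethasone, or its absence, consistently wherever the maintenance regimen is described. Define the denominator for Section 3.3.5 as the reconciled schedule for the patient's age group. The investigators decide which dose applies.

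The cost is protocol wording only; the sample size and primary analysis stay as they are.

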## 4.2 Number of Patients

Approximately 40 patients will be enrolled and treated on study.

## 4.3 Duration of Study

Patients will receive D-ClaPd at a dose defined by the treatment plan for up to 30 cycles, unless one of the following occurs:

- Disease progression
- Intercurrent illness that prevents further administration of treatment
- Unacceptable adverse event(s) defined as:

Occurrence of an AE that is related to treatment with the study drug which, in the judgment of the investigator, compromises the patient's ability to continue study-specific procedures, or is considered to not be in the patient's best interest.

Persistent AE requiring a delay of therapy for more than 4 weeks (28 days).

- Patient decides to withdraw from the study
- General or specific changes in the patient's condition render the patient unacceptable for further treatment in the judgment of the investigator
- Patient becomes pregnant
- Patient loses the ability to freely provide consent through imprisonment or involuntary incarceration for treatment of a psychiatric or physical illness
- Patient achieves complete remission (CR), and the patient and investigator feel that discontinuation is in the patient's best interests, or
- Patient achieves a level of response that qualifies him or her for another therapy, such as high dose therapy with autologous stem cell transplantation, and the patient and investigator feel that discontinuation is in the patient's best interests

#### Follow-up

At the completion or early discontinuation of treatment, patients will be followed for an additional 90 days after the last administration of treatment or up until the initiation of the next line of treatment, whichever comes first. Patients with adverse events will be followed until the event has resolved or the condition has stabilized

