#### Post Treatment Observation Phase

Patients who discontinue study treatment before disease progression has been observed, will undergo disease evaluations every 90 days (+/- 30 days) as specified in the Post-Treatment Observation Phase in the Study Calendar for a duration of 24 months or until confirmed hematologic disease progression, whichever comes first.

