### **7.4 Post-Treatment Observation Phase**

For patients who complete all 32 cycles of treatment on study, if have not progressed or started new treatment, patients will be followed with disease evaluations every 90 days (+/- 30 days) until confirmed disease progression or for total duration of 24 months from last EOT visit, whichever comes first, and for OS for up to 10 years from date of enrollment or until death.

Patients who discontinue study treatment before disease progression has been observed, will undergo disease evaluations every 90 days (+/- 30 days) as specified in the Post-Treatment Observation Phase in the Study Calendar for a duration of 24 months or until confirmed hematologic disease progression, whichever comes first.

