##### Response

Parameters assessed will include stringent complete response (sCR), complete response (CR), very good partial response (VGPR), partial response (PR), and stable disease (SD) per standard IMWG response criteria. In addition, overall response rate (defined as greater than or equal to PR across all cycles of treatment), response duration, time-to-response (TTR), MRD negativity rate and improvement in response during maintenance therapy will be assessed.

Best overall response categories will be tabulated and overall for CR, VGPR, PR, SD, progressive disease, and relapse. A two-sided 95% exact binominal CI will be calculated for each category. The response rate (responses  $\geq$  PR) will also be tabulated. Time-to-event analyses will be done using Kaplan- Meier analyses and will include time to response, duration of response, PFS, and OS, as data allow. If there is not enough data to apply the Kaplan-Meier test, the data will be summarized by descriptive statistics.

Time to response (for responders only) will be calculated as the time from the date of first study treatment dosing to the first date of documented response (PR or better) and will be summarized by descriptive statistics.

Duration of response (for responders only) is defined as the time from the earliest date of documented response (PR or better) to the earliest date when disease progression was confirmed. Patients who are non-responders will be excluded from this analysis. Detailed censoring rules for duration of response will be specified in the SAP.

PFS will be calculated as the time from the initial administration of Daratumumab, Clarithromycin, Pomalidomide, and Dexamethasone until documented disease progression, as determined using standard response criteria, or death from any cause, whichever occurs first. Kaplan-Meier methods will be used to estimate PFS over time and the median duration of PFS. Patients with no PFS event will be censored at the date of their last disease assessment.

Time to next therapy is defined as the time from the initial administration of Daratumumab, Clarithromycin, Pomalidomide, and Dexamethasone on trial to next treatment.

OS is defined as the time from the initial administration of Daratumumab, Clarithromycin Pomalidomide and Dexamethasone to death from any cause. Kaplan-Meier methods will be used to estimate the OS function. Patients who do not die will be censored at the date that the patient was last known to be alive.

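### Survival follow-up is written only for patients who complete 32 cycles; patients who progress on treatment have none beyond 90 days or next therapy, so OS is open to informative censoring, probably upward

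*Combined protocol and SAP*

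**What the plan says.** Follow-up after treatment is described in several places, and the rule differs by how the patient leaves treatment.

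- **Completers.** Section 7.4 begins "For patients who complete all 32 cycles of treatment on study, if have not progressed or started new treatment" and, after the disease-evaluation clause, ends "and for OS for up to 10 years from date of enrollment or until death". Participant Duration in the Protocol Summary has the same structure and ends "and for survival for up to 10 years from date of enrollment or until death". Survival follow-up is mentioned nowhere else.
- **Stopped before progression.** Section 4.3, Post Treatment Observation Phase: "Patients who discontinue study treatment before disease progression has been observed, will undergo disease evaluations every 90 days (+/- 30 days"). Section 7.4 repeats the limit: "Post-Treatment Observation Phase in the Study Calendar for a duration of 24 months or until confirmed hematologic disease progression, whichever comes first". Section 7.5 places transplant patients in the same phase for the same period.
- **Everyone leaving treatment, including those who progress on it.** Section 4.3, Follow-up: "followed for an additional 90 days after the last administration of treatment or up until the initiation of the next line of treatment", whichever is first.

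The Schedule of Study Procedures has no survival row, and its post-treatment column runs for 24 months or until progression. Section 9.2.1.1 limits SAE reporting, the route by which deaths are reported, to 30 days after the last dose.

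OS runs from first dose to death from any cause and is estimated by Kaplan-Meier. Section 8.1.6 states: "Patients who do not die will be censored at the date that the patient was last known to be alive".

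The number of cycles that defines a completer is not consistent. Section 4.3 has treatment "at a dose defined by the treatment plan for up to 30 cycles", section 7.4 and Participant Duration use 32, and section 6.11 uses 12.

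**The concern.** Kaplan-Meier estimation assumes that a patient censored at a given time has the same later risk of death as those still followed. Here the event that ends follow-up is, for most patients, progression on treatment or the start of another therapy. If death is more frequent after progression than before it, the high-risk patients drop out of the risk set and the curve is carried by those who have not progressed. Median OS is a stated secondary objective and would then be reported too high.

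Time to next therapy, also secondary, shares the gap. A patient who progresses and starts new treatment after day 90, or who stops early and is observed only until progression, has no planned contact at which that date would be recorded.

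**Working it through.** **1. The plan's own figure.** The only design calculation concerns the primary endpoint: at least 8 of 40 with VGPR or better, null 9%, target 25%. Exact binomial: P(X ≥ 8 | 40, 0.09) = 0.024 and P(X ≥ 8 | 40, 0.25) = 0.818, which meets the stated 5% and 80%. It does not depend on survival follow-up. No event count, power or expected value is given for OS.

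**2. How many patients reach the 10-year follow-up.** 32 cycles × 28 days = 896 days ≈ 29.4 months. With exponential PFS and no other discontinuation, the share progression-free at that time is 2^(−29.4/median PFS). The medians are those quoted in section 1.1.

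- 7.7 months (ClaPd): 2^(−3.82) = 7.1%, about 3 of 40.
- 4 months (pomalidomide/dexamethasone, phase 3): 2^(−7.35) = 0.6%, fewer than 1 of 40.
- 4.2 months (pomalidomide/dexamethasone, phase 2): 2^(−7.0) = 0.8%, fewer than 1 of 40.

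**3. Effect on the OS curve.** Illness-death simulation, 400,000 patients per scenario. PFS is exponential at the medians above. Post-progression survival is exponential, set so that true median OS equals the value in section 1.1 (19.3, 12.7 or 16.5 months). Patients who progress before 29.4 months are censored at 90 days or next therapy; completers are followed to 120 months. Assumptions not in the documents: 5% to 30% of PFS events are deaths, and 50% or 100% of progressors start new therapy 0.5 to 3 months after progression. The stopping rule in section 8.1.7 is not modelled.

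| Median PFS / true median OS (months) | KM median, 5–30% deaths | KM median, 20% deaths | KM median, 30% deaths | 24-month OS: as written vs true |
|---|---|---|---|---|
| 7.7 / 19.3 | 23.4–39.8 | 28.5–30.2 | 23.4–23.6 | 49–72% vs 39–41% |
| 4 / 12.7 | 13.0–24.0 | 15.5–16.4 | 13.0–13.1 | 28–50% vs 19–26% |
| 4.2 / 16.5 | 14.8–32.8 | 18.9–19.3 | 14.8 | 33–61% vs 32–38% |

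Deaths would be observed in about 16% to 42% of patients (0.16 × 40 ≈ 6 to 0.42 × 40 ≈ 17), against 99% to 100% with full 10-year follow-up. Full follow-up recovers the true median in every scenario.

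**4. Why the direction can change.** If a share d of PFS events are deaths, the death hazard before progression corresponds to a median of (median PFS)/d. The bias is upward when this exceeds the post-progression median. At d = 30%:

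- 7.7/0.3 = 25.7 against 14.0 months: upward.
- 4/0.3 = 13.3 against 12.1 months: almost none.
- 4.2/0.3 = 14.0 against 19.1 months: slightly downward.

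At d = 10% with PFS 7.7 the comparison is 77 against 9.4 months, hence the large upward bias.

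**5. Does the 24-month rule for early stoppers help?** Adding 2% per month stopping before progression (PFS 7.7, OS 19.3, 10% deaths), and following them for 24 months or until progression, gives a KM median of 37.9 to 40.1 months against a true 19.3. It does not, because that observation also ends at progression.

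**The case against.** The best defence is that this is awkward drafting, not a decision to stop counting deaths. The survival clause runs from enrollment, whereas the disease-evaluation clause beside it runs from the end-of-treatment visit. OS is defined without any completion condition. The 90-day rule in section 4.3 applies to completers too, so it cannot be meant to end all follow-up; section 7.3 describes the 90 days as a watch for late toxicity. Censoring at last known alive allows chart or phone updates. Time to next therapy and the rule in section 8.1.7 that stops the study after more than four deaths both presuppose some tracking.

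Much of this stands as evidence of intent. It does not supply a procedure: no section or Schedule row requires a survival contact after a patient progresses on treatment, and a site following the text would make none.

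A reader might also infer that everyone except completers is followed for only 90 days. The documents do not support that: sections 4.3, 7.4 and 7.5 give patients who stop before progression, and transplant patients, up to 24 months of evaluations. Nor does the 30-cycle limit in section 4.3 show that nobody was meant to have survival follow-up. That is a separate inconsistency, though it leaves the eligible group undefined.

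**Conclusion.** The concern holds in a limited form. Planned survival follow-up covers few patients, and loss of follow-up for the others is triggered mainly by progression or new therapy, so the OS censoring is informative if the plan is followed as written. The bias is probably upward. It ranges from about a doubling of the median (39.8 against 19.3 months) to nothing or a small reversal (13.0 against 12.7; 14.8 against 16.5), mainly according to the unknown share of PFS events that are deaths. All these figures rest on exponential times and on the assumptions listed with the table.

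Two stronger conclusions are tempting and unsupported. One is that OS will certainly be heavily inflated: the 30% scenarios show otherwise, and informal vital-status updates would reduce the bias. The other is that a false comparison with historical OS is built in: section 4.1 compares only the VGPR rate (9%) and ORR (60%) with history, and OS has no test or threshold. This is a defect in an untested secondary endpoint, worth correcting early because contacts not made may not be recoverable at analysis.

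**What to change.** In section 4.3, section 7.4, Participant Duration and the Schedule, state that every treated patient is followed for survival and for the date of next therapy until death or 10 years from enrollment, regardless of the reason for stopping, progression or new therapy. A phone or chart check every 3 to 6 months is enough. Add a survival row to the Schedule, and say how the 90-day period in section 4.3 relates to the later observation and survival phases.

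Reconcile the maximum number of cycles across section 4.3 (30), section 7.4 and Participant Duration (32) and section 6.11 (12).

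The cost is a short amendment and the added contact work over several years. No visits or tests are added, and the primary analysis and sample size do not change.
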